10.2. Statistical Methodology

A summary of the data will be prepared for all measurement time points.

For variables measured on a continuous scale, these summaries will include the sample size, as well as the mean, standard deviation, median, minimum, and maximum. For variables measured on a categorical scale, summaries will provide the number and percentage of subjects in each category. These summaries will be provided for all eyes completing the study.

The difference in the aspiration time between groups will be used to test the non-inferiority hypothesis. If the upper boundary of the 95th confidence interval is not greater than 23, non-inferiority will be claimed. In the event that non-inferiority is demonstrated, then a test of superiority will be performed.

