3. GENERAL INFORMATION

Objective	To assess the efficiency of the Active Sentry handpiece at low intraocular pressure (IOP) compared with the Ozil at high IOP. The Active Sentry handpiece at low IOP (20 mmHg) is as efficient as Ozil at high (50mmHg).
Test Article(s)	Active Sentry® Handpiece
Control Article(s)	None.
Sample size	70 eyes of 35 subjects
Study Population	Subjects \geq 50 years of who are eligible to undergo sequential bilateral uncomplicated cataract surgery.
Number of sites	One
Study Design	Single site, single-masked, randomized, prospective contralateral eye study.
Masking	The data analyzer will be masked.
Variables	Primary: The total aspiration time between groups on day of surgery. Secondary: 
• Total fluid volume between groups on day of surgery.• Total phaco time between groups on day of surgery.• Total case time between groups on day of surgery.• Aspiration time during phaco between groups on day of surgery.• Central corneal thickness (CCT) between groups at postoperative day 1 and week 1.
Duration / Follow-up	Preoperative to 1 week postoperative

The study will be registered with clinicaltrials.gov.

The study will be conducted in compliance with the protocol, GCP and applicable regulatory requirements

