7. SUBJECTS

7.1. *Subject Population*

Eligible test subjects will be 50 years of age or older and who are eligible to undergo sequential bilateral uncomplicated cataract surgery.

A total of 70 eyes of 35 subjects at one site will be enrolled. Both eyes of a subject must be enrolled. Subjects must meet the inclusion criteria. Prior to enrollment, subjects will be provided information on the study and asked to sign a patient information and consent form to participate. The patient information and consent form will be approved by an appropriate ethics committee.

7.2. *Inclusion Criteria*

Subjects are eligible for the study if they meet the following criteria:

Note: Ocular criteria must be met in both eyes.

- Be eligible to undergo sequential bilateral uncomplicated cataract surgery.
- Undergo uneventful cataract surgery.
- Gender: Males and Females.
- Both eyes must have same grade of cataract.
- Willing and able to provide written informed consent for participation in the study.
- Willing and able to comply with scheduled visits and other study procedures.

7.3. *Exclusion Criteria*

If any of the following exclusion criteria are applicable to the subject or either eye, the subject should not be enrolled in the study.

- Patient under 50 years of age.

- Unable to complete sequential bilateral cataract surgery in both eyes by the same surgeon (JS).
- Patient cataract surgery complicated by posterior capsular tear.
- Any disease state deemed by PI that increases risk of complicated cataract surgery (ie Pseudoexfoliation syndrome, zonular dehiscence, history of eye trauma, RA, prior refractive surgery, etc).

The principal investigator reserves the right to declare a patient ineligible or non-evaluable based on medical evidence that indicates they are unsuitable for the trial.

Pregnancy has a known effect on the stability of refractions and visual acuity. As such, subjects who become pregnant during the study will not be discontinued but their data may be excluded from analyses of effectiveness.

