8. STUDY DESIGN

8.1. Study Design

This study is a single site, single-masked, randomized, prospective, contralateral eye study of the efficiency of the Active Sentry handpiece at low IOP compared with the Ozil at high IOP. Subjects will be assessed pre-operatively, operatively and at 1 day and 1 week post-operatively. Clinical evaluations will include measurement of visual acuity and central corneal thickness (CCT).

The primary outcome measure will be the total aspiration time between groups on day of surgery.

Secondary outcome measures are as follows:

- Total fluid volume between groups on day of surgery.
- Total phaco time between groups on day of surgery.
- Total case time between groups on day of surgery.
- Aspiration time during phaco between groups on day of surgery.
- Central corneal thickness (CCT) between groups at postoperative day 1 and week 1.

Exploratory outcome measures are as follows:

- Cumulative dissipated energy between groups on day of surgery.

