10. ANALYSIS PLAN

10.1. Analysis Data Sets

All subjects who are enrolled in the study will be evaluated for safety. Efficacy analyses will be performed based on data from those eyes where uncomplicated cataract surgery was completed.

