11. SAMPLE SIZE JUSTIFICATION

Assuming a pooled standard deviation of 36.8^5 seconds and a mean difference of 0 seconds, the study would require a sample size of: 32 for each group (i.e. 64 eyes of 32

subjects), to achieve a power of 80% and a level of significance of 5%, for declaring that the Active Sentry is not inferior to the Ozil at 23 seconds margin of non-inferiority. To account for drop outs a total of 35 subjects (70 eyes) will be recruited.

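### Each patient contributes one eye to each arm, but section 11 sizes the trial as independent groups and section 10.2 does not say that the primary interval is computed within patient

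*Combined protocol and SAP*

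**What the plan says.** Section 8.1 describes a "single site, single-masked, randomized, prospective, contralateral eye study", and section 7.1 adds "Both eyes of a subject must be enrolled". Section 7 also requires the same cataract grade in both eyes and the same surgeon for both.

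Section 11 sizes the trial as follows: "Assuming a pooled standard deviation of 36.8^5 seconds and a mean difference of 0 seconds", leading to "a sample size of: 32 for each group (i.e. 64 eyes of 32" subjects. Power is 80%, the significance level 5% and the margin 23 s; 35 subjects are recruited to allow for dropout. I read the 5 after 36.8 as a reference mark, not an exponent.

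Section 10.2 states the primary analysis in two sentences: "The difference in the aspiration time between groups will be used to test the non-inferiority hypothesis", and "If the upper boundary of the 95th confidence interval is not greater than 23, non-inferiority will be claimed". A superiority test follows if non-inferiority is shown. Section 10.3 adds the software and an alpha of 0.05. Section 10.1 defines the efficacy set by eye: "Efficacy analyses will be performed based on data from those eyes where uncomplicated cataract surgery was completed".

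**The concern.** The two groups are the same patients. The variance of the difference in means therefore contains the covariance between fellow eyes, and a valid interval has to include it. Sections 10.1 to 10.3 name no within-patient difference, paired test or model with a patient effect. The only calculation shown, in section 11, uses a pooled SD and a count per group, with no correlation and no SD of differences.

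The primary conclusion depends on one upper limit against 23 s, so the choice of standard error can decide it. With positive correlation an unpaired interval is too wide and power is lost. With negative correlation it is too narrow and non-inferiority is claimed too often. If a paired interval is used, section 11 does not give the power of the test performed. The superiority test has the same gap.

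**Working it through.** **Inputs.** SD 36.8 s, true difference 0, margin 23 s, power 80%, 32 per group from 32 subjects (section 11); 95% interval rule (section 10.2). The between-eye correlation ρ is not in the documents, so every value below is an assumption. I take 36.8 s as the SD of single eyes, which is how the word pooled reads.

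**Step 1: reproduce the 32.** Independent groups: n = 2 × 36.8² × (z_α + 0.8416)² / 23².
- One-sided 5% (z = 1.645): 31.65, rounded up to 32, which matches.
- One-sided 2.5% (z = 1.960, equivalent to a two-sided 95% interval): 40.19, so 41, which does not match.

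If 36.8 s were the SD of within-patient differences, the count would be 16 pairs at one-sided 5% or 21 at 2.5%. Neither matches.

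**Step 2: the two intervals, 32 pairs, two-sided 95%.**
- Unpaired half-width: t(0.975, 62) × 36.8 × √(2/32) = 1.999 × 9.2 = 18.4 s at any ρ.
- Paired half-width: t(0.975, 31) × SD_d / √32, where SD_d = 36.8 × √(2(1 − ρ)) and t = 2.040.

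Paired power comes from the noncentral t distribution. Unpaired power and error come from simulated bivariate normal data, 400,000 runs per setting. Error is the chance of claiming non-inferiority when the true difference is 23 s; the nominal value is 2.5%.

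| ρ (assumed) | SD_d (s) | Half-width paired (s) | Half-width unpaired (s) | Power paired | Power unpaired | Error if unpaired |
|---|---|---|---|---|---|---|
| 0.3 | 43.5 | 15.7 | 18.4 | 82% | 73% | 1.0% |
| 0.5 | 36.8 | 13.3 | 18.4 | 93% | 76% | 0.3% |
| 0.7 | 28.5 | 10.3 | 18.4 | 99% | 81% | 0.03% |

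At ρ = −0.2, SD_d is 57.0 s. The correct half-width is 20.6 s against 18.4 s unpaired, and the unpaired error is 3.6%.

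**Step 3: same data, two answers.** At ρ = 0.5, an observed difference of 7 s gives an upper limit of 7 + 13.3 = 20.3 s paired, which passes, and 7 + 18.4 = 25.4 s unpaired, which fails.

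**Step 4: power of a paired two-sided 95% rule.** With 32 pairs it is 68%, 77%, 82% and 93% at ρ = 0, 0.2, 0.3 and 0.5. It reaches 80% only from ρ = 0.25, or from 0.18 with all 35 pairs.

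**Step 5: sidedness, a separate matter.** Under independence, 32 per group gives 80% power at one-sided 5% but 69% under a two-sided 95% interval. If the 95% limit is read as a one-sided bound, paired power with 32 pairs is 79%, 90% and 96% at ρ = 0, 0.3 and 0.5.

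**The case against.** The strongest reply is that this is an omission, not a wrong analysis. No unpaired test is named, section 11 sizes the trial rather than specifying the analysis, and counting 64 eyes of 32 subjects shows that the planners knew the eyes were paired. That is fair: the text permits an unpaired interval but does not prescribe one.

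A paired formula with ρ = 0 also returns 31.65, so the independent-groups formula is not the only possible source of the 32. But that too sizes the trial as though fellow eyes were unrelated. At section 11's own one-sided 5%, 32 pairs is about enough at ρ = 0 and more than enough at positive ρ, so pairing does not make the trial too small. This stands.

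Same patient, grade and surgeon all point to positive correlation. Lost power is then the realistic harm, and the 3.6% error at ρ = −0.2 is a less likely case. This stands too.

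The ρ = 0.25 threshold depends on reading the interval as two-sided, which section 10.2 does not say. Both readings are therefore shown above.

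On single eyes, section 7.3 excludes a subject if a criterion applies to either eye and lists posterior capsular tear, which suggests removing the whole patient. Sections 9.2.2 and 10.1 do not settle this: the former only allows exclusion of performance data, and the latter works by eye. The conflict is a further reason to write a rule.

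None of this supplies the missing method.

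**Conclusion.** The concern holds and should be fixed. The design is paired, the sample size has no term for pairing, and the primary interval is not defined as within-patient. On a two-sided 95% reading with 32 pairs and an SD of 36.8 s, an unpaired interval gives up roughly 9 to 18 percentage points of power at correlations of 0.3 to 0.7 (82 − 73, 93 − 76, 99 − 81). The stated 80% is not the power of a paired test under that rule; depending on correlation, that power is below or above 80%.

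This rests on assumed correlations, normal data and 36.8 s being a per-eye SD. The source marked 5 is not in the reference list as supplied, so the last assumption cannot be confirmed. That no within-patient method is specified depends on none of these.

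**What to change.** - **Section 10.2.** Define the primary estimate as the mean within-patient difference in total aspiration time, Active Sentry eye minus Ozil eye, with a two-sided 95% paired t interval. Claim non-inferiority if its upper limit does not exceed 23 s. Use the same within-patient difference for the superiority test and for any test of a secondary outcome, with corneal thickness handled separately at day 1 and week 1.
- **Section 10.1.** State that the primary interval uses patients with both eyes in the efficacy set. As a sensitivity analysis, fit a mixed model with handpiece fixed and patient random to all eyes in the set, so that patients with one evaluable eye are kept. Reconcile this with the either-eye exclusion in section 7.3.
- **Section 11.** Restate power for 32 pairs from an SD of differences, or over a stated range of correlations, at the alpha of the interval rule. For a two-sided 95% interval these are the figures in step 4.

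**Cost.** Wording in three sections; no new data or visits. Because the documents give no correlation, section 11 has to show a range. If fellow eyes are uncorrelated, pairing costs about one point of power (68% against 69%). Using complete pairs only costs little: with 29 pairs and 3 single eyes per arm at ρ = 0.5, the standard error is 36.8/√29 = 6.83 s, against 6.66 s by generalised least squares on all eyes.

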9. STUDY PROCEDURE

9.1. *Informed Consent / Subject enrollment*

No subject will be enrolled into the study who does not meet the inclusion/exclusion criteria and does not sign the current approved informed consent document. Informed consent will be obtained prior to collecting any data for the study. The original signed documents will be maintained by the investigator as a permanent part of the subject's medical records. A signed copy will be provided to the subject.

9.2. *Visits and Examinations*

Subjects will participate in 7 study visits, including one visit for screening. Visits will include an uptake visit, two operative visits, and 4 postoperative visit (Visit numbers 1-4 and 2a, 3a, and 4a below). The visit schedule, complete with window and associated CRF forms, are displayed in Table 9.2-1. Details of each study visit, including testing to be conducted, are provided below.

Table 9.2-1. Visit Schedule

Visit Number	Visit Name	Visit Window	CRF Number
1	Preoperative	-90 to 0 days from surgery	1
2	Operative	0 from surgery	2
3	1 Day Postoperative	1-2 days postoperative	3
4	1 Week Postoperative	7 days (± 3) postoperative	4
2a	Operative*	0 from surgery	2a
3a	1 Day Postoperative*	1-2 days postoperative	3a
4a	1 Week Postoperative*	7 days (± 3) postoperative	4a

*second eye

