9.2.2. Operative (Surgery)

All subjects will undergo sequential bilateral cataract surgery. The surgeon's usual standard of care with regard to treatment and medication will be used for all study subjects. Surgery planning will be performed using the surgeon's preferred method.

Surgical findings will be recorded and will include the tests below:

- Total phaco time,
- Total aspiration time,
- Total fluid volume,
- Total case time,
- Cumulative dissipated energy

Any adverse events/serious adverse events (AEs/ SAEs) occurring during surgery will be noted at this visit. Any other problems during surgery and comments regarding surgery will be documented.

Any subject whose surgery is not completed successfully will be documented in the appropriate case report form. These subjects will be monitored for safety but clinical performance data may be excluded from the analysis.

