10.3. General Statistical Considerations

The statistical analyses will be performed using R, version 4.1.2 or higher. Any statistical tests of hypotheses will employ a level of significance of alpha=0.05.

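### Section 10.2 leaves out patient and surgery order (first or second eye), although order is recorded; a mixed model with both would be a cheap gain in precision

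*Combined protocol and SAP*

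**What the plan says.** The primary analysis is set out in section 10.2 of the combined protocol and SAP: "The difference in the aspiration time between groups will be used to test the non-inferiority hypothesis". The decision rule follows: "If the upper boundary of the 95th confidence interval is not greater than 23, non-inferiority will be claimed". No model, pairing or covariate is named there, and section 10.3 adds only the software and "Any statistical tests of hypotheses will employ a level of significance of alpha=0.05".

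The design makes surgery order a known factor. Section 9.2.2 states: "All subjects will undergo sequential bilateral cataract surgery". Section 9.2 describes the schedule: "Visits will include an uptake visit, two operative visits, and 4 postoperative visit (Visit numbers 1-4 and 2a, 3a, and 4a below". Table 9.2-1 marks visits 2a, 3a and 4a as belonging to the second eye. Table 15.1 collects total aspiration time separately under First Eye (Visit 2) and Second Eye (Visit 2a), so order is available for every eye.

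Section 8.1 calls the study randomised and contralateral. It does not say whether handpiece is randomised to eye or to order, or whether order is balanced. Section 10.1 defines the efficacy set by eye, not by patient.

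**The concern.** Each patient contributes one eye per handpiece, and one eye always comes first. If second eyes take systematically more or less aspiration time than first eyes, every within-patient handpiece difference carries that order effect with a plus or minus sign.

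Leaving order out has two consequences. The order effect enters the residual variance and widens the interval. If the two orders are not equally frequent among the evaluable pairs, part of it also enters the estimate in that particular trial. The conclusion depends on whether one upper limit clears 23 seconds, so both matter in principle. The variable that would remove them is already collected.

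**Working it through.** **Inputs from the documents.** Section 11 gives the SD and true difference ("Assuming a pooled standard deviation of 36.8^5 seconds and a mean difference of 0 seconds"; the raised 5 is a citation mark, so the SD is 36.8 s), the power and level ("to achieve a power of 80% and a level of significance of 5"%, sidedness not stated) and the margin ("not inferior to the Ozil at 23 seconds margin of non-inferiority"). It asks for 32 per group and recruits 35 patients.

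**Inputs assumed.** The documents give no first-to-second-eye difference p and no between-eye correlation ρ. I use p = 5, 10 and 20 s and ρ = 0.5, and show ρ = 0.3 for comparison. The interval is read as two-sided 95%.

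**The plan's own figure.** Two independent groups, normal approximation, one-sided 5%:

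n = 2 × 36.8² × (1.645 + 0.842)² / 23² = 31.7, rounded up to 32.

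This reproduces the stated size. At one-sided 2.5% the same formula gives 40.2, that is 41. The calculation has no pairing and no order component.

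**Model.** Let d be Active Sentry minus Ozil within a patient, and p the second-eye minus first-eye difference. Then d = τ + s·p + e, with s = +1 if Active Sentry was used second and −1 if first, and SD(e) = 36.8 × √(2(1 − ρ)). At ρ = 0.5 this SD is 36.8 s.

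**Effect on the interval.** At an even split of 32 pairs, ignoring order gives a variance of 36.8² + p² × 32/31. For p = 20 s: 1354.2 + 412.9 = 1767.1, an SD of 42.04 s. Half-widths, with 31 degrees of freedom unadjusted and 30 adjusted:

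| p (s) | Order ignored (s) | Order fitted (s) | Widening |
|---|---|---|---|
| 5 | 13.39 | 13.29 | 0.8% |
| 10 | 13.76 | 13.29 | 3.6% |
| 20 | 15.16 | 13.29 | 14% |

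**Power.** Simulated with 32 pairs, τ = 0 and order drawn at random for each patient:

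| p (s) | ρ = 0.5, ignored | ρ = 0.5, fitted | ρ = 0.3, ignored | ρ = 0.3, fitted |
|---|---|---|---|---|
| 0 | 93% | 92% | 82–83% | 81% |
| 5 | 92–93% | 92% | 82% | 81% |
| 10 | 91% | 92% | 81% | 81% |
| 20 | 85% | 92% | 75% | 81% |

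Because order is drawn at random, these figures already contain the effect of uneven splits.

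**Shift in a given trial.** The estimate moves by p × (n1 − n2)/N. With 35 pairs:

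- 18:17 split: 10 × 1/35 = 0.29 s at p = 10 s.
- 22:13 split: 10 × 9/35 = 2.57 s at p = 10 s, and 20 × 9/35 = 5.14 s at p = 20 s.

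If order were allotted by simple 1:1 randomisation, 22:13 or worse would occur with probability 0.175.

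**Error rate.** With the true difference at 23 s, random order and 32 pairs, the unadjusted rule falsely claims non-inferiority about 2.5% of the time at p = 10 and 20 s, the same as the adjusted rule. Given a realised 22:13 split of 35 pairs and p = 10 s, the unadjusted rate is about 5% if the imbalance favours Active Sentry and 0.8% if it goes the other way. With the order term it is about 2.5% in both cases.

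**The case against.** The strongest objection is that the size rests on an input the documents do not contain. Both eyes must have the same cataract grade (section 7.2) and one surgeon operates on both (section 7.3), so a small order effect is quite possible. At 5 s or less the term gains nothing and may cost a fraction of a point. An effect of 20 s would be close to the whole margin. This objection stands, and it limits how much weight the point can bear.

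A second objection is that section 10.2 is silent on order and pairing and does not prescribe an unpaired or unadjusted test. That also stands. If the eyes were analysed as two independent groups, as in the sample-size formula, order would matter even less: the half-width goes from 18.39 s to 18.56 s at p = 10 s and 19.06 s at 20 s. The unstated pairing would then be the larger matter.

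A reader might infer that the plan's estimate is biased, or its error rate inflated. The documents do not support this. Under random order the shift is chance imbalance that averages to zero, and overall false non-inferiority stays near 2.5%. The shift would be systematic only if one handpiece were tied to first or second surgery, which nothing in the protocol states. Nor should the shift be added to the power loss as a second harm, because the power figures already include it.

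What survives is that order is known and its omission can only be repaired credibly before the data are seen. Even a balanced allocation can become uneven, because section 10.1 excludes eyes individually, and 35 pairs cannot split evenly.

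**Conclusion.** The point holds as a precision improvement of minor to moderate importance that also protects against an uneven realised split. It is not an error in the plan. On the stated assumptions (SD 36.8 s, ρ = 0.5, 32 pairs, random order, two-sided 95% limit), fitting order changes power by no more than about 1 point for p up to 10 s and recovers about 7 points at 20 s. At ρ = 0.3 the recovery at 20 s is about 6 points. Neither p nor ρ can be taken from the documents, so whether the trial falls in the negligible or the material range is unknown.

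**What to change.** In section 10.2, state that the handpiece difference in total aspiration time is estimated from a linear mixed model with handpiece and surgery order (first or second eye) as fixed effects and patient as random effect. Apply the 23-second rule to the upper confidence limit of that estimate, and use the same model for the other operative outcomes.

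With complete pairs this matches regressing the within-patient difference on order coded +1/−1 and taking the intercept. The mixed model is preferable because the by-eye efficacy set in section 10.1 can leave unpaired eyes. The model can be fitted only if handpiece is not tied to order, so the protocol should state how the two are allocated.

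The cost is a sentence or two in the SAP, no new data and one degree of freedom. If there is no order effect, the loss is about 1 percentage point of power (93% to 92% at ρ = 0.5).
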